Potential advantages of neoadjuvant therapy include downsizing and/or downstaging of tumors to change surgical approach from radical to partial nephrectomy or from open to minimally invasive surgery, and to allow for resection of unresectable tumors and potentially sparing organs. Lane et. reported presurgical sunitinib in 72 patients with renal cell carcinoma (11). Median tumor size improved from 7.2 cm to 5.3 cm after sunitinib treatment. Downsizing occurred in 65 tumors (83%), with 15 partial responses (19%) (11). 41% of patients with nephrometry score >9 could undergo partial nephrectomy, and eGFR change was -16% in partial nephrectomy group vs -24% in radical nephrectomy group (11). Rini et al. reported a phase II study of pazopanib in patients with localized renal cell carcinoma (12). 6 out of 13 patients for whom partial nephrectomy not possible at baseline underwent successful partial nephrectomy (12). Karam et al reported neoadjuvant axitinib in biopsy proven locally advanced clear cell renal cell carcinoma patients. In this cohort, all patients were T3a, and received up to 12 weeks of axitinib without any grade 3-4 adverse events. 11/24 patients achieved partial response, 13/24 patients achieved stable disease, and no disease progression were observed. The increased response rates for cabozantinib in mRCC above, along with the neoadjuvant axitinib data where 45% of neoadjuvantly treated patients achieved partial response, strongly support an expanded role for cabozantinib in the neoadjuvant setting.

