2 STUDY OBJECTIVES AND ENDPOINTS

The objectives of this study are as follows:

Primary objective:

- To assess the objective response rate (complete and partial responses), following the administration of cabozantinib for 12 weeks in patients with locally advanced biopsy-proven non-metastatic ccRCC prior to undergoing surgery.

Secondary Objectives:

- To assess the safety, and tolerability of neoadjuvant cabozantinib.
- To determine the clinical outcome (DFS, OS) of patients with non-metastatic ccRCC who treated with neoadjuvant cabozantinib.
- To evaluate the surgery related outcomes.
- To evaluate correlative studies, including biomarkers, quality of life, and frailty/sarcopenia assessment of patients with non-metastatic ccRCC who are treated with neoadjuvant cabozantinib.

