9 STATISTICAL CONSIDERATIONS

The primary outcome is objective response rate (complete and partial responses) at week 12 after the administration of cabozantinib. The Simon's two-stage design will be adopted for a possible early termination for futility. We hypothesize that there is > 24% response rate at 12-week and a rate < 5% will be considered as futility. In the first stage, 11 patients will be accrued (this does not include screen failures), and if there is no responses among them, the study will be stopped for futility. Otherwise, additional 6 patients will be accrued for a total of 17 patients. The null hypothesis will be rejected if there are 3 or more responses in 17 patients. The design yields a type I error rate of 0.05 and power of 80% when the true response rate is 24%. The final response rate will be estimated with 95% confidence interval by binomial test.

The safety profile of the treatment will be documented and summarized by summary statistics as frequency and percentage for each AE. We will do safety assesment after the first 6 patients without pausing the enrollment.

For disease free survival (DFS), which was defined as the interval between time of surgery and the first tumor recurrence, or death. Patients will be censored at time of last follow-up. For overall survival, death from any cause will be defined as the event. Patients will be censored at time of last follow-up. Overall survival (OS) and disease free survival (PFS) will be estimated

with the Kaplan-Meier method. The DFS and OS of each patient group at specific time points, such as 6 months, 1 year, and 3 year, etc. will be also estimated along with 95% CI.

For the biomarker study, descriptive statistics will be first used to summarize biomarker endpoints, including analyses of tumor biopsies. Biomarker data will also be displayed graphically, where appropriate. Depending on whether data is normally distributed, t-test or Wilcoxon rank sum test will be used to compare each biomarker between any two groups stratified by response or other factors, respectively. Logistics regression model will be further employed to test the adjusted effect of biomarker on the response rate after adjusting for other factors.

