12.4 Correlative studies

Paired tissue will be collected at baseline from all 17 patients either archival tissue or within 28 days before Week 1 day 1 after consent is signed. Tissue will be obtained during surgery as post treatment. The obtained tissues will be handled in the following way:

- 1) RNAlater for RNA stabilization and tissue storage
- 2) Formalin-fixed paraffin block with one cut H&E stained slide
- 3) Liquid nitrogen frozen tissue in cryo-preservation vials

All collected tissues are stabilized and stored in -80°C freezers (RNAlater stabilized, OCT embedded, short term storage) or the vapor phase of a liquid nitrogen freezer (long term storage) in single use aliquots. All FFPE tissue blocks are stored in a climate-controlled storage room that is temperature (less than 27°C) and humidity controlled.

Tissue will be evaluated using IHC or immunofluorescence to measure relevant immune markers (i.e. CD3, CD4, CD8, CD163, PD-1, PD-2, PDL-1, MIF, TAM and stromal/ vascular markers, MET, others). When sufficient quantities of fresh tissue is available, it will also be dissociated and flow cytometry will be used to determine the phenotypic characteristics of cell populations in the tumor microenvironment. Tissue will be preserved for future exploratory studies including genomic profiling.

Peripheral blood samples

Approximately 60 mL of peripheral blood will be collected prior to initiation of study therapy (at baseline), week 6 day 1 (+/-5 days), the completion of treatment prior to surgery and post-surgical resection (Table 5-1). The peripheral blood mononuclear cells will be isolated from these samples and stored in -80°C freezers until analysis. Plasma will be stored in -80°C freezers until analysis.

Samples will be evaluated including but not limited to:

- i. Determine whether there are phenotypic changes in of T-cell or myeloid cell surface markers (including co-stimulatory/immune checkpoint molecules) in PBMCs after treatment.
- ii. Determine whether functional changes are evident in PBMCs in response to treatment and whether these data correlate with clinical outcome measures. Pending quantity of cells a variety of assays may be performed, including but not limited to intracellular cytokine production and expression of CD107.
- iii. Assess ctDNA quantity and analysis in plasma samples at baseline and the completion of treatment prior to surgery.

Shipping and handling instructions

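### The adjusted biomarker–response logistic regression in at most 17 patients has no stated fitting method; under default maximum likelihood its tests would be miscalibrated, and Firth-penalised fitting should be specified

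*Combined protocol and SAP*

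**What the plan says.** Section 2 lists the correlative work among the secondary objectives: "To evaluate correlative studies, including biomarkers, quality of life, and frailty/sarcopenia assessment of patients with non-metastatic ccRCC". Section 9 sets out the biomarker analysis in order: descriptive summaries and graphs, then a t-test or Wilcoxon rank sum test of each biomarker between groups such as responders and non-responders, then a model: "Logistics regression model will be further employed to test the adjusted effect of biomarker on the response rate after adjusting for other factors".

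The sample size was set for the response rate alone. On stage 1, Section 9 says: "In the first stage, 11 patients will be accrued (this does not include screen failures), and if there is no responses among them", the trial stops. It continues: "Otherwise, additional 6 patients will be accrued for a total of 17 patients". The rates behind the design are given as: "We hypothesize that there is > 24% response rate at 12-week and a rate < 5% will be considered as futility". Section 12.4 confirms the ceiling on biomarker data: "Paired tissue will be collected at baseline from all 17 patients". Its list of tissue markers is open-ended.

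Neither Section 9 nor any other section names the adjustment covariates, limits their number, says how the logistic model is fitted or which test is read from it, or says what happens when the fit has no finite solution.

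**The concern.** A logistic model with a biomarker and one covariate estimates three parameters. With about 4 responders, the large-sample theory behind the ordinary likelihood-ratio and Wald tests cannot be relied on, and the two can fail in opposite directions. The same data could then yield an adjusted association or none, depending on which test the software prints. The unnamed covariates add a second choice that could be made after the data are seen. A reported odds ratio could also be inflated. What is at stake is one secondary, correlative claim: that a biomarker relates to response after adjustment.

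**Working it through.** **1. Reproduce the design.** The null is rejected with at least 1 response in the first 11 and at least 3 in 17. So P(reject) = P(at least 3 of 17) − P(0 of 11) × P(at least 3 of 6).
- At 5%: 0.0503 − 0.5688 × 0.0022 = 0.0490.
- At 24%: 0.8123 − 0.0489 × 0.154 = 0.8048.

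These match the stated 0.05 and 80%. They concern the response rate only.

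**2. Expected responders.** 17 × 0.24 = 4.1. Section 1 says of neoadjuvant axitinib that "45% of neoadjuvantly treated patients achieved partial response"; at that rate, 17 × 0.45 = 7.7. Ignoring the stage 1 stop, the chance of 4 or fewer responders in 17 is 61% at 24% and 6% at 45%. Since 24% is the lower edge of the hypothesised range, both 4 and 8 responders were examined.

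**3. Simulation set-up.** The documents give no biomarker distribution and no covariates, so these are assumptions: n = 17 with exactly 4 or 8 responders; biomarker N(0,1); log odds ratio 0 or 1.0 per SD (odds ratio e^1.0 = 2.72); 4,000 data sets per setting; two-sided 5% tests. The prognostic covariate has its own log odds ratio of 1.0 and correlation 0.5 with the biomarker; the other covariates have no effect. Separation (no finite estimate) was checked by linear programming. Separated fits count as Wald non-rejections and are left out of the maximum-likelihood (ML) medians. Monte Carlo standard error for test sizes is about 0.3–0.5 percentage points.

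**4. Results under maximum likelihood.** Each cell gives 4 responders / 8 responders. The last three columns are for a true log odds ratio of 1.0.

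| Covariates | LR size, % | Wald power, % | Median log-OR | Separated, % |
|---|---|---|---|---|
| None | 7.6 / 6.6 | 3.8 / 18.2 | 1.17 / 1.12 | 2.0 / 0.4 |
| One normal | 8.8 / 7.7 | 1.5 / 13.4 | 1.23 / 1.21 | 5.3 / 1.3 |
| One binary | 9.2 / 8.8 | 1.8 / 13.9 | 1.20 / 1.22 | 16.4 / 2.3 |
| Two normal | 12.5 / 9.6 | 0.3 / 8.1 | 1.26 / 1.30 | 13.2 / 4.7 |
| One prognostic | 10.1 / 9.4 | 0.3 / 3.2 | 1.21 / 1.24 | 14.8 / 7.7 |

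Wald size is 0.6% or less at 4 responders and 0.4–1.5% at 8. At 4 responders the ML estimate exceeds 2.0, twice the true value, in 23–29% of fits. A median of 1.26 corresponds to an odds ratio of e^1.26 = 3.5 for a true 2.7.

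**5. Results under Firth**, with the penalised-likelihood-ratio test, over the same settings:
- Size 3.8–4.5% at 4 responders and 4.0–4.9% at 8.
- Median log odds ratio 0.83–0.90 and 0.89–0.91 for a true 1.0.
- Estimate above 2.0 in 11–12% of fits at 4 responders.
- Power 26–31% and 36–38% with no covariate or one independent covariate; 14% and 21% with the correlated prognostic one.

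**6. Separate runs.** With the number of responders left random at a 24% rate and one normal covariate (8,000 data sets), size was 9.9% for LR, 0.3% for Wald and 3.7% for Firth. In a run of 1,000 data sets at 4 responders with one covariate and a true log odds ratio of 1.0, LR rejected in 38% and Wald in 1%. One LR size came out near nominal: 5.5% in 1,500 data sets at 8 responders with one normal covariate. Three other runs of that setting gave 7.4%, 7.7% and between 8.6% and 8.7%.

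**7. The unadjusted tests.** In 1,500 data sets, null size was 5.1% (t-test) and 4.4% (exact Wilcoxon) at 4 responders, and 6.7% and 6.1% at 8, where Firth gave 5.9% on the same data. Another run gave 3.2–5.4%. Power at a log odds ratio of 1.0, in the order t-test / Wilcoxon / biomarker-only Firth, was 31 / 27 / 28% at 4 responders and 42 / 38 / 39% at 8.

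**The case against.** Four stronger readings are tempting, and the documents do not support them.

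- **That the plan has chosen a wrong method.** Section 9 says only logistic regression, and a Firth fit is also logistic regression. The supportable statement is conditional: the method is unstated, and the usual default performs badly here.
- **That the biomarker analysis as a whole is unsound.** The adjusted model comes after a t-test or Wilcoxon comparison, and those hold their size acceptably at this sample size. The unadjusted call does not depend on the choice between LR and Wald; only the adjusted claim does.
- **That calibration demands at most one covariate.** In a 1,500-data-set run, Firth size with 1 / 2 / 3 covariates was 4.2 / 3.7 / 3.7% at 4 responders and 5.3 / 5.4 / 4.9% at 8. Power fell gradually: 26 / 23 / 21% and 36 / 34 / 32%. A cap is a judgement about power and post-hoc choice.
- **That a biomarker-only Firth fit would improve testing.** It has no more power than the tests already planned; it adds an odds ratio with an interval.

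It is also fair to say that every distribution in the simulation is assumed and that only a normal biomarker was examined. Inflation at 8 responders with one independent normal covariate is modest. The median comparison is not like for like, since ML omits separated fits and Firth uses all data sets. With no covariate at 8 responders the two medians miss by similar amounts (1.12 against about 0.9). Firth's clearer advantages are test size, fewer extreme estimates and behaviour once covariates enter.

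What survives is that the plan commits to an adjusted test, and an ordinary fit of it would give a misleading p-value.

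**Conclusion.** The concern holds for the adjusted biomarker–response test, on the condition that it is fitted by maximum likelihood. With one or two covariates, LR size is about 8–13% at 4 responders and 7–10% at 8. Wald size is about 1.5% or less, with power under 2% at 4 responders for a log odds ratio of 1.0. The estimate tends to overstate a real effect. The direction was consistent across the runs; the exact percentages depend on the assumed number and type of covariates.

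A reader might infer that the trial's main conclusions are exposed. They are not: the primary response analysis, the stage 1 rule, safety, DFS and OS use none of this. This is a point to consider, confined to one secondary correlative objective.

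**What to change.** In Section 9, specify that the adjusted biomarker–response model is fitted by Firth-penalised logistic regression, with a penalised-likelihood-ratio test and a profile-likelihood 95% confidence interval, and is reported as exploratory. Name the covariate or covariates before biomarker data are read. Keeping to one is advisable, to protect power and limit post-hoc choice, but it is optional. Keep the t-test or Wilcoxon as the unadjusted test. Exact logistic regression is not a general substitute: with one continuous covariate its reference set shrank to a single arrangement in 300 of 300 simulated data sets at both 4 and 8 responders.

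The cost is wording only; samples and data are unchanged. Three limits remain:
- Power stays low, about 24–40% at a log odds ratio of 1.0 and less with a correlated prognostic covariate.
- The Firth median is slightly low, about 0.83–0.91 for a true 1.0.
- Multiplicity across the open-ended marker list is not addressed by the fitting method.

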10 DATA AND SAFETY MONITORING PLAN

The Data and Safety Monitoring Committee (DSMC) of the Winship Cancer Institute will provide oversight for the conduct of this study. The DSMC functions independently within

Winship Cancer Institute to conduct internal monitoring functions to ensure that research being conducted by Winship Cancer Institute Investigators produces high-quality scientific data in a manner consistent with good clinical practice (GCP) and appropriate regulations that govern clinical research. Depending on the risk level of the protocol, the DSMC review may occur every 6 months or annually. For studies deemed High Risk, initial study monitoring will occur within 6 months from the date of the first subject accrued, with 2 of the first 5 subjects being reviewed. For studies deemed Moderate Risk, initial study monitoring will occur within 1 year from the date of the first subject accrued, with 2 of the first 5 subjects being reviewed. Subsequent monitoring will occur in routine intervals per the Winship Data and Safety Monitoring Plan (DSMP).

The DSMC will review pertinent aspects of the study to assess subject safety, compliance with the protocol, data collection, and risk-benefit ratio. Specifically, the Winship Cancer Institute Internal Monitors assigned to the DSMC may verify informed consent, eligibility, data entry, accuracy and availability of source documents, AEs/SAEs, and essential regulatory documents. Following the monitoring review, monitors will provide a preliminary report of monitoring findings to the PI and other pertinent individuals involved in the conduct of the study. The PI is required to address and respond to all the deficiencies noted in the preliminary report. Prior to the completion of the final summary report, monitors will discuss the preliminary report responses with the PI and other team members (when appropriate). A final monitoring summary report will then be prepared by the monitor. Final DSMC review will include the final monitoring summary report with corresponding PI response, submitted CAPA (when applicable), PI Summary statement, and available aggregate toxicity and safety data.

The DSMC will render a recommendation and rating based on the overall trial conduct. The PI is responsible for ensuring that instances of egregious data insufficiencies are reported to the IRB. Continuing Review submissions will include the DSMC recommendation letter. Should any revisions be made to the protocol-specific monitoring plan after initial DSMC approval, the PI will be responsible for notifying the DSMC of such changes. The Committee reserves the right to conduct additional audits if necessary.

[name] and the investigators, the clinical research coordinator and the regulatory affairs coordinator will meet to review and discuss study data to ensure subject safety. During the meetings the PI or co-I will review the eligibility criteria for each new patient. In addition, during these meeting the group will review all the toxicity (AE/SAE) logs, random checks of case report form completion and roadmap for each patient on the trial. All study personnel will be trained on the protocol by the PI or co-I. Study personnel will sign training log prior to being included on delegation of authority log. All AE and SAE will be handled according to Section 8.2 which provides detailed instructions on reporting requirements.

11 STUDY COMMITTEES

N/A

12 ETHICAL ASPECTS

12.1 Local Regulations

The study must fully adhere to the principles with the FDA GCP (Good Clinical Practice). The investigator will ensure that the conduct of the study complies with the basic principles of GCP as outlined in the current version of 21 Code of Federal Regulations, subpart D, Part 312, “Responsibilities of Sponsors and Investigators” Part 50, “Protection of Human Subjects” and Part 56, “Institutional Review Boards.”

12.2 Informed Consent

It is the responsibility of the investigator, or a person designated by the investigator, to obtain written informed consent from each subject participating in this study after adequate explanation of the aims, methods, anticipated benefits, and potential hazards of the study. In the case where the subject is unable to read, an impartial witness should be present during the entire informed consent discussion. After the subject has orally consented to participation in the trial, the witness’s signature on the form will attest that the information in the consent form was accurately explained and understood.

If new safety information results in significant changes in the risk/benefit assessment, the consent form should be reviewed and updated as necessary. All subjects (including those already being treated) should be informed of the new information, should be given a copy of the revised form, and should give their consent to continue in the study.

12.3 Institutional Review Board/Ethics Committee

This protocol (and any modifications) and appropriate consent procedures must be reviewed and approved by an IRB/EC. This board must operate in accordance with current local, regional, and federal regulation

s. The investigator will send a letter or certificate of IRB/EC approval to Exelixis (or designee) before subject enrollment and whenever subsequent modifications to the protocol are made.

12.4 Correlative studies

Paired tissue will be collected at baseline from all 17 patients either archival tissue or within 28 days before Week 1 day 1 after consent is signed. Tissue will be obtained during surgery as post treatment. The obtained tissues will be handled in the following way:

- 1) RNAlater for RNA stabilization and tissue storage
- 2) Formalin-fixed paraffin block with one cut H&E stained slide
- 3) Liquid nitrogen frozen tissue in cryo-preservation vials

All collected tissues are stabilized and stored in -80°C freezers (RNAlater stabilized, OCT embedded, short term storage) or the vapor phase of a liquid nitrogen freezer (long term storage) in single use aliquots. All FFPE tissue blocks are stored in a climate-controlled storage room that is temperature (less than 27°C) and humidity controlled.

Tissue will be evaluated using IHC or immunofluorescence to measure relevant immune markers (i.e. CD3, CD4, CD8, CD163, PD-1, PD-2, PDL-1, MIF, TAM and stromal/ vascular markers, MET, others). When sufficient quantities of fresh tissue is available, it will also be dissociated and flow cytometry will be used to determine the phenotypic characteristics of cell populations in the tumor microenvironment. Tissue will be preserved for future exploratory studies including genomic profiling.

Peripheral blood samples

Approximately 60 mL of peripheral blood will be collected prior to initiation of study therapy (at baseline), week 6 day 1 (+/-5 days), the completion of treatment prior to surgery and post-surgical resection (Table 5-1). The peripheral blood mononuclear cells will be isolated from these samples and stored in -80°C freezers until analysis. Plasma will be stored in -80°C freezers until analysis.

Samples will be evaluated including but not limited to:

- i. Determine whether there are phenotypic changes in of T-cell or myeloid cell surface markers (including co-stimulatory/immune checkpoint molecules) in PBMCs after treatment.
- ii. Determine whether functional changes are evident in PBMCs in response to treatment and whether these data correlate with clinical outcome measures. Pending quantity of cells a variety of assays may be performed, including but not limited to intracellular cytokine production and expression of CD107.
- iii. Assess ctDNA quantity and analysis in plasma samples at baseline and the completion of treatment prior to surgery.

Shipping and handling instructions

After appropriate processing, the blood samples, tissue blocks, slides or frozen tissue samples will be sent to:

[name] Laboratory
[name]
[name]
ph: [name]
email: [contact]

On the day that the specimens are to be shipped, notify [name] of the pending specimen shipments. Include the Fed-Ex tracking number in the email.

Research blood contact Information:

[name] Laboratory
ph: [name]
email: [contact]

Quality of life will be studied using the Functional Assessment of Cancer Therapy-Kidney Specific Index-19 (FKSI-19) questionnaire (Appendix C), which will be filled out at baseline, on weeks 6, and 12 after treatment initiation.

Frailty assessment will be studied using the Fried Frailty score (Appendix D), which will be obtained at baseline, on week 6, and 12 after treatment initiation.

Sarcopenia assessment will be done by using baseline and week 12 scans via SliceOmatic v5.0 by TomoVision program.

